9.2 Data handling and record keeping

The anonymised Excel Data Tools will be submitted by each centre and received by the PMT. The anonymised data from each local Excel Data Tool will be combined into a master national Excel Data Tool, with each update saved as a separate version and old versions retained.

Anonymised data may be made available to applicants who submit a project proposal to the project PMT, and which subsequently receives approval from: the PMT, and the INTEGRATE committee.

10 Statistics and data analysis

This study is an audit of current practice which will be judged against pre-specified standards derived from relevant published guidelines:

- British Association of Head and Neck Oncologists (BAHNO) standards, 2020 (15)
- 'Streamlining NHS Multidisciplinary Team Meetings: Guidance for Cancer Alliances', NHS England and NHS Improvement 2020 (16)
- 'NHS Cancer Programme: Faster Diagnosis Framework', NHS England and NHS Improvement from 2022, although first published in 2019 (17)
- Head and Neck Cancer: United Kingdom National Multidisciplinary Guidelines, BAHNO 2016 (18)

10.1 Sample size

The final sample size will be dependent on the number of centres submitting data and so there is no a priori estimation.

10.2 Pooled analysis

All cases will be entered into a pooled analysis. No individual centre will be identifiable from the analysis.

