The British Association of Head and Neck Oncologists (BAHNO) produced their first guideline on the management of HN cancers in 2002. In 2020 it published its most recent guideline "British Association of Head and Neck Oncologists (BAHNO) standards 2020" (15), which set out to establish standards for HN MDTs UK-wide, as well as encourage sharing of knowledge between different MDTs. Anecdotally there is variation in practice amongst MDTs throughout the country, with some more oncologically-orientated and others more surgically-orientated. Standardising HN MDTs is difficult due to regional variation in resources and demographic characteristics. As such, this protocol outlines a national retrospective audit to understand the decision-making process for patients with HN cancer across the United Kingdom, focusing specifically on HNSCC that comprises the majority of diagnoses.

5 Aim and objectives

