5.3 Secondary Objectives

- 1. To gain an understanding of the variation in HN MDT recommendations
- 2. To evaluate the 2-year overall, disease-specific and disease-free survival outcomes, and recurrence rates of head and neck cancers
- 3. To audit UK-wide HNSCC pathways and their compliance with cancer waiting targets, including identifying delays and potential areas for improvement
 - a. 28 days 'Faster Diagnosis Standard' (FDS) for primary HNSCC
 - b. 31 days from the referral to decision-to-treat
 - c. 62 days from referral to the commencement of treatment (31 days for recurrent HNSCC)
- 4. To examine the use of local anaesthetic biopsy for histological diagnosis and its impact on pathway timings
- 5. To assess the HN MDT workforce against national guidelines

6 Study design and setting

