10.5 Statistical analysis

Patient demographic data will be presented with mean and SD for continuous variables and counts and proportions for categorical variables. Categorical data will be analysed with the Chi-square or Fisher's Exact test as appropriate. Quantitative continuous variables will be analysed using descriptive statistics such as

mean, standard deviation, median, quartiles, minimum/maximum and range. Continuous variables will be assessed with Student's t-test, Mann-Whitney U test, Kruskal-Wallisor the Wilcoxon test as appropriate.

Survival curves will be produced using the Kaplan-Meier method. Sensitivity analyses will be undertaken. Comparison of survival outcomes for sub-groups will be performed using the log rank test and Cox Proportional Hazard model.

11 Ethical considerations

This audit will report on the outcomes of investigative management that has already taken place. There will be no effect on the management of patients as a result of inclusion in the study. All data will be anonymised, and no patients will be identifiable in any subsequent reports, presentations or publications. As such, consent from individual patients will not be required.

This project has been determined to be an audit using the HRA decision tool available at http://www.hra-decisiontools.org.uk/research/ (Appendix 1). The output from this process is available in the Appendix. This should be discussed locally for study participation approval on request.

Local centres are asked to register the audit with their audit department and/or Caldicott guardian, in keeping with local protocol.

12 Authorship policy

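### All centres are pooled and tested as if patients were independent, and no between-MDT measure is named for the objective on variation in recommendations

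*Protocol*

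**What the plan says.** Section 10.2 fixes the structure of the analysis: "All cases will be entered into a pooled analysis. No individual centre will be identifiable from the analysis". Section 10.5 fixes the methods:

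- For categorical data: "Categorical data will be analysed with the Chi-square or Fisher's Exact test as appropriate".
- For continuous data: "Continuous variables will be assessed with Student's t-test, Mann-Whitney U test, Kruskal-Wallisor the Wilcoxon test as appropriate".
- For survival: "Comparison of survival outcomes for sub-groups will be performed using the log rank test and Cox Proportional Hazard model".

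No centre term, stratification by centre, random effect, frailty or robust variance is mentioned. Section 10.5 adds only "Sensitivity analyses will be undertaken", without content.

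Secondary objective 1 (section 5.3) is "To gain an understanding of the variation in HN MDT recommendations". Section 4 explains why it is there: "Anecdotally there is variation in practice amongst MDTs throughout the country", with some MDTs leaning towards oncology and others towards surgery.

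**The concern.** The outcome of interest is a decision taken by the MDT. Patients of one MDT share the decision-maker, the local resources and the diagnostic pathway, so their outcomes are likely to be correlated. The protocol's own rationale presumes this. The tests in section 10.5, applied to a pooled file with no allowance for centre, take each patient as a separate piece of information.

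Two things are at stake. First, statements about the UK, such as the proportion managed in line with guidelines (primary objective 2) or treated within target (secondary objective 3), would look more precise than they are. Comparisons by centre characteristics would also reach significance too easily. Section 8.6 collects several such characteristics: unit type, MDT frequency, platform, same-day clinic and specialties present. Second, a pooled result shows the average recommendation and not how far MDTs depart from it, so secondary objective 1 has no analysis that matches it.

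**Working it through.** **Plan's own figures.** Section 10.1 gives no sample size, and the protocol states no number of centres, significance level or ICC, so there is no design figure to reproduce. The one relevant figure, cluster size, agrees with its own input in section 8.8: 200 SCC per year / 4 = 50 per three months.

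**Inputs.**
- Cluster size m = 50: section 8.8, an upper figure for a mid-large MDT. m = 20 and m = 10 are assumptions for smaller units.
- ICC of 0.01 to 0.10: assumption.
- Two-sided 5% level (z = 1.96): assumption.
- 40 centres, used only in the simulation: assumption.

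**Formulas.**
- Design effect DE = 1 + (m − 1) × ICC.
- Factor by which the naive standard error is too small = √DE.
- True error of a nominal 5% test of a factor that is constant within centre = 2 × (1 − Φ(1.96/√DE)).
- Coverage of a naive 95% interval for an overall proportion = 1 minus that error.

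Example, m = 50 and ICC = 0.05: DE = 1 + 49 × 0.05 = 3.45; √3.45 = 1.86; 1.96/1.86 ≈ 1.055; error = 2 × (1 − Φ(1.055)) = 29.1%; coverage = 70.9%.

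| m | ICC | DE | SE factor | Error, centre-level test | Coverage, overall proportion |
|---|---|---|---|---|---|
| 50 | 0.01 | 1.49 | 1.22 | 10.8% | 89.2% |
| 50 | 0.02 | 1.98 | 1.41 | 16.4% | 83.6% |
| 50 | 0.05 | 3.45 | 1.86 | 29.1% | 70.9% |
| 50 | 0.10 | 5.90 | 2.43 | 42.0% | 58.0% |
| 20 | 0.01 | 1.19 | 1.09 | 7.2% | 92.8% |
| 20 | 0.02 | 1.38 | 1.17 | 9.5% | 90.5% |
| 20 | 0.05 | 1.95 | 1.40 | 16.0% | 84.0% |
| 20 | 0.10 | 2.90 | 1.70 | 25.0% | 75.0% |
| 10 | 0.01 | 1.09 | 1.04 | 6.0% | 94.0% |
| 10 | 0.10 | 1.90 | 1.38 | 15.5% | 84.5% |

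At m = 50, an illustrative 1000 pooled patients carry the information of 1000/DE = 671, 505, 290 or 169 independent ones as the ICC rises from 0.01 to 0.10.

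**Simulation.** Pooled chi-square without continuity correction; 40 centres; beta-binomial outcome with mean 0.5; 4000 runs per setting; no true effect. Rejection rate at nominal 5%:

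| Factor compared | m | ICC 0.01 | ICC 0.05 | ICC 0.10 |
|---|---|---|---|---|
| Constant within centre (e.g. unit type) | 50 | 11.1% | 29.5% | 41.4% |
| Constant within centre | 20 | 7.1% | 17.0% | 25.5% |
| Patient-level, balanced within centre | 50 | 4.8% | 4.0% | 3.5% |
| Patient-level, prevalence varies by centre (assumed exposure ICC 0.10) | 50 | 5.4% | 8.3% | 11.2% |
| Patient-level, prevalence varies by centre (same assumption) | 20 | 5.4% | 5.9% | 7.6% |

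The first two rows confirm the formula. In the last two rows, exposure prevalence was drawn independently of the centre's outcome level, so they show the variance problem only. If centres that use local anaesthetic biopsy more often are also faster or slower for other reasons, bias would be added; that is not quantified here.

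**Objective against method.** The five sub-groups listed in section 10.3 are defined by the patient, the tumour or the biopsy, and none by centre or unit type. Section 10.5 names no between-centre quantity. The data areas listed in section 8.6 include unit type but no centre code, although the full dataset sits in the Excel Data Tool, which is not shown.

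**The case against.** The strongest reply is that this is a descriptive audit. It states no hypothesis, significance level or sample size, and its appendix answers no to generalisable findings. For describing the participating centres alone, the pooled proportion is the right estimate and clustering matters little. Centre effects are also the kind of detail that a SAP may add, and only the protocol is at hand. This stands in part. But section 5.1 sets the aim as management in the UK, section 10.5 plans hypothesis tests, and the protocol itself fixes both the pooling and the test families.

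A reader might infer three stronger claims, none of which the protocol supports.

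- *That the plan cannot answer secondary objective 1.* The sentence on identifiability repeats the confidentiality commitment of section 8.1 and does not say that the centre variable is dropped. Each centre submits its own file (section 9.2), so a code can be kept, and the sub-group list in section 10.3 is open. Recommendation by coded centre could even be tested with the chi-square of section 10.5. That would give a p-value and not the size of the variation, and nothing commits the analysts to doing it.
- *That every standard error is wrong.* Patient-level contrasts balanced within centres remain valid or slightly conservative.
- *That the protocol commits to the misleading results.* Section 10 promises no confidence intervals and names no comparison by unit type or MDT format. The large error rates describe analyses that the collected data invite, not ones that the plan states.

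**Conclusion.** The point holds in a bounded form. The plan pools clustered patients, names only tests that assume independence, and provides no measure of between-MDT variation for secondary objective 1.

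The gap in objective 1 follows from the text and needs no assumption. The size of the inferential error does rest on assumptions. Any interval for an overall UK proportion, or any test of a centre-level factor, would be too optimistic. At 50 cases per unit and an ICC of 0.01 to 0.10, standard errors are too small by a factor of about 1.2 to 2.4, and a nominal 5% centre-level test errs about 11% to 42% of the time. At 20 cases per unit the ranges are 1.09 to 1.70 and 7% to 25%. Fifty is a ceiling and the ICC is not in the protocol; with an ICC of zero there is no error.

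Patient-level comparisons are little affected unless the factor varies by centre. Local anaesthetic biopsy (secondary objective 4) may do so, with simulated error of about 5% to 11% at 50 per unit. That simulation used a binary outcome, so it speaks most directly to compliance with a waiting target.

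**What to change.** - **Data (sections 8.6 and 9.2):** state that a pseudonymised centre code is kept in the master dataset. This identifies neither hospitals nor patients in any report, so it is compatible with sections 8.1, 8.5 and 10.2.
- **Proportions, times and comparisons (section 10.5):** use centre-clustered robust variance or a centre random intercept, with a small-sample correction if few centres take part.
- **Survival (section 10.5):** use a Cox model stratified by centre, with shared frailty or with robust variance.
- **Secondary objective 1:** for a short list of key recommendations, report the between-centre variance as an ICC or median odds ratio, adjusted for case mix (for example subsite, stage, performance status and age), without labelling centres.

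The cost is one code column, revised wording in sections 10.2 and 10.5, and slightly more analysis work. Intervals will be wider. No further patient data are needed, because origin is known when each centre's file arrives.

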10.3 Sub-group analysis

Sub-group analysis may include, but not be limited to:

- Patients with primary and recurrent HNSCCs, respectively
- Patients with HPV-positive and negative oropharyngeal tumours, respectively, confirmed via p16 immunocytochemistry or fluorescent in-situ hybridisation
- Patients with a histologically confirmed primary HNSCC with an N3 neck nodal staging
- Patients with a histologically confirmed primary or recurrent HNSCC and an additional synchronous primary or recurrent HNSCC
- Patients with a histologically confirmed primary HNSCC who had diagnostic biopsy performed under local anaesthetic in the outpatient clinic

10.4 Analysis exclusion criteria

Patients for whom 2-year follow-up data is unavailable will not be included in the subsequent 2-year follow-up analysis.

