8.2 Patient identification

Local investigators will obtain a list of consecutive patients from their centres for inclusion into the study.

These patients will:

have had a diagnosis of primary or recurrent HNSCC

AND

- have been discussed at MDT

AND

- have had a definitive 'decision to treat' for their primary or recurrent HNSCC documented via their MDT outcome between 1st September 2021 and 30th November 2021.

Local investigators are advised to acquire patient lists via their H&N MDT co-ordinators. Where a patient list is obtained via an MDT coordinator, it is recommended that the list is limited to the most recent discussion date for each patient, so that final MDT outcomes can be retrieved following investigations. 2-year follow-ups for these patients will then be retrieved by local investigators where available.

Where necessary, the PMT will be able to further guide local investigators upon request: [contact]

The MDT notes and 2-year outcomes for all patients will be reviewed by the local team and full eligibility criteria applied. All eligible patients will be recorded onto an Excel Data Tool. All screened patients and any reasons for exclusions will be recorded.

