8.6 Dataset

The full dataset is delineated in the study Excel Data Tool. This tool will collect data in the following areas:

- Demographics and referral details: demographics; smoking status; alcohol status; ECOG performance status; source of referral
- MDT details: unit type (tertiary referral or district general); frequency of MDT; platform; same-day clinic; specialties present; allied healthcare professionals
- Cancer pathway dates: date of referral; date of first specialist clinic; date of biopsy; date of MDT outcome; date patient was informed of diagnosis; date treatment commenced; FDS
- Diagnostic biopsies: date of biopsy(s); subsite(s); anaesthesia; location (clinic or operating theatre)
- Imaging for diagnosis: modality, body site
- Diagnosis: subsite; clinical T stage; clinical N stage; clinical M stage; TNM 8; new or recurrence; p16 and HPV status; EBV status; PDL-1 status; presence of clinical ENE; presence of synchronous head and neck tumour
- Presence of synchronous HNSCC: subsite; clinical T stage; TNM 8; new or recurrence; p16 and HPV status; EBV status; PDL-1 status
- **Treatment:** modality of treatment (including surgical and/or oncological technique, timings or doses); treatment intent
- **Recurrence:** recurrent or residual disease; nature of recurrence (local, regional or distant); timing of recurrence after completion of treatment; treatment of recurrence
- Surveillance: timing of post-treatment surveillance imaging; modality
- Follow-up: time to last follow-up and/or death; cause of death

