9.1.3 Missing data

The PMT will check the submitted data for completeness and integrity. If necessary, the PMT will give feedback to the local team where any data fields are inadequate. The submitting team will be asked to provide the missing data where possible. If data is not available, the data point will be treated as null, and that record will be excluded from any subsequent relevant analysis where necessary.

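### Section 10.4 deletes patients without 2-year follow-up data instead of censoring them; if deaths before 2 years stay in, 2-year overall survival is understated when loss is unrelated to prognosis

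*Protocol*

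**What the plan says.** Secondary objective 2 in Protocol section 5.3 is "To evaluate the 2-year overall, disease-specific and disease-free survival outcomes, and recurrence rates of head and neck cancers". Four parts of the protocol bear on how this is estimated.

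- Section 10.4 sets the exclusion: "Patients for whom 2-year follow-up data is unavailable will not be included in the subsequent 2-year follow-up analysis". It has no exception for patients with partial follow-up.
- Section 10.5 sets the estimator, "Survival curves will be produced using the Kaplan-Meier method", and the subgroup methods: "Comparison of survival outcomes for sub-groups will be performed using the log rank test and Cox Proportional Hazard model". It promises sensitivity analyses but names none.
- Section 8.6 lists the follow-up item collected: "time to last follow-up and/or death; cause of death".
- Section 8.2 accepts that follow-up may be incomplete: "2-year follow-ups for these patients will then be retrieved by local investigators where available".

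Section 9.1.3 points the same way as 10.4, since a record with an unavailable data point is dropped from the relevant analysis. The protocol does not define 2-year follow-up data, does not say how deaths before 2 years are handled under 10.4, and gives no censoring rule.

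**The concern.** Kaplan-Meier and Cox methods exist to use incomplete follow-up. A patient seen alive at month 18 and not again contributes 18 event-free months and is then censored. Section 10.4 removes that patient altogether. A patient who died at month 5 has a known status at 2 years and stays. Whether a patient is analysed therefore depends partly on the outcome: among patients whose follow-up would have stopped early, those who died first are kept and those still alive are not.

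At stake are the 2-year survival figures of secondary objective 2 and the subgroup comparisons built on them. This is not a detail left for a statistical analysis plan. The protocol fixes a rule, and a later plan that censored these patients would contradict it.

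**Working it through.** **The plan's own figure.** There is none to reproduce. The protocol states no survival rate, no loss rate and no sample size (section 10.1). All rates below are assumptions.

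**Which reading of 10.4.** If deaths before 2 years were also dropped for want of a 2-year record, everyone left would be alive at 2 years and overall survival would be 100% by construction. Since overall survival is an objective and time to death is collected, the workable reading keeps those deaths. This is an inference; the protocol does not say it.

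**Loss independent of prognosis.** Let S be true 2-year survival and L the probability that the loss time falls before 2 years, with independent exponential death and loss times:

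- death rate λ = −ln(S)/2; loss rate μ = −ln(1−L)/2
- alive and followed to 2 years: a = exp(−2(λ+μ)) = S(1−L)
- death observed before 2 years: d = λ/(λ+μ) × (1−a)
- removed by 10.4: 1 − a − d
- estimate under 10.4: a/(a+d)

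Example with S = 0.65 and L = 0.20: λ = 0.2154, μ = 0.1116, a = 0.65 × 0.80 = 0.520, d = 0.2154/0.3270 × 0.480 = 0.316. Removed: 1 − 0.520 − 0.316 = 0.164. Estimate: 0.520/0.836 = 0.622.

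| Assumed L | Estimate under 10.4 (true 65%) | Error, points |
|---|---|---|
| 5% | 64.4% | −0.6 |
| 10% | 63.7% | −1.3 |
| 20% | 62.2% | −2.8 |
| 30% | 60.4% | −4.6 |

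Kaplan-Meier with all patients kept and the lost ones censored gives about 65% in this setting.

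Simulations of 400,000 patients per scenario at other assumed survival rates agree with the formula. Over true survival of 60, 70 and 80% and loss of 5 to 30%, the understatement runs from about 0.5 to 5 points, while censoring recovers the true value to within 0.1 point. In every scenario the Kaplan-Meier value under 10.4 equals the crude proportion alive, because no one is censored before 2 years.

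The error also depends on prognosis. At L = 20%, a true 60% becomes 57.0% (−3.0) and a true 80% becomes 78.0% (−2.0). Subgroups are thus shifted unequally even when their loss rates match.

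**Loss confined to survivors.** If a fraction c of survivors lack 2-year data and no patient who died does, the estimate under 10.4 is S(1−c)/(S(1−c)+1−S). With S = 0.65:

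- c = 0.10: 0.585/0.935 = 62.6%
- c = 0.20: 0.520/0.870 = 59.8%
- c = 0.30: 0.455/0.805 = 56.5%

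This loss is informative, so censoring is biased too. With c = 0.20 and survivors' loss times assumed uniform over 0 to 2 years, Kaplan-Meier with censoring gives about 62.3%. Of the 5.2-point error (65.0 − 59.8), about 2.5 points (62.3 − 59.8) are recovered and about 2.7 remain.

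**The case against.** The strongest reply is that 10.4 may be meant more narrowly: leave out patients with no retrievable follow-up record and censor the rest. Sections 8.2, 8.6 and 10.5 are compatible with that, and dropping patients with no follow-up time adds no bias under independent loss. This stands as a possible intention. It is not what 10.4 says, because its condition is the absence of 2-year data, not the absence of any follow-up. If the narrow meaning is intended, the text still has to be changed.

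The second reply is about size. Collection opens on 1 December 2023, between 2.00 and 2.25 years after the MDT decisions of 1 September to 30 November 2021, so no patient is administratively short of 2 years from that decision. The workload table in section 8.8 has the same ceiling of 50 patients per unit for eligibility and for 2-year follow-up. Ceilings are not a loss estimate, but nothing in the protocol supports loss of 20 to 30%, and at 5% the error is under 1 point. This stands: the size is unknown and may be small.

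Three stronger inferences are tempting and are not supported:

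- A reader might infer that the whole 5.2-point error under survivor-only loss disappears once patients are censored. About half of it remains.
- A reader might infer that loss differs between tertiary and other units and so distorts subgroup comparisons. The protocol collects unit type but says nothing about differential loss, and unit type is not among the subgroups listed in section 10.3, although that list is open-ended.
- A reader might infer that Kaplan-Meier loses its purpose throughout. That holds for overall survival. For disease-specific survival, deaths from other causes may still be censored, so the method keeps some function.

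**Conclusion.** Section 10.4 is wrong as written and should be fixed. Followed literally, and with early deaths kept, it makes inclusion depend on the outcome and reduces the 2-year Kaplan-Meier estimate of overall survival to a crude proportion.

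Under loss independent of prognosis the direction is downward. At an assumed true 65%, the error is about 0.6 points at 5% loss and 4.6 at 30%, and censoring removes essentially all of it. Loss confined to survivors gives a larger error that censoring only partly removes. Other patterns of informative loss could change the direction.

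The figures concern overall survival; disease-specific survival, disease-free survival and recurrence come under the same rule but were not quantified. The consequence is limited to secondary objective 2 and its subgroup comparisons. The primary objectives and the waiting-time, biopsy and workforce objectives are not affected.

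**What to change.** Replace section 10.4 with a rule to this effect: all eligible patients with any follow-up time enter the survival analyses; patients without an event are censored at last follow-up (for disease-free survival, at last follow-up without recorded recurrence); follow-up is administratively censored at 2 years. State that deaths before 2 years count as events for overall survival. Make clear that the general rule in section 9.1.3 does not override this.

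Report the number of patients censored before 2 years and the number with no follow-up at all, so that readers can judge how far informative loss could matter. Keep the complete 2-year subset only as a named sensitivity analysis.

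The cost is a short rewrite of 10.4. Time to last follow-up or death is already listed in section 8.6, so overall survival needs no new data item. Section 8.6 lists no separate date on which a patient was last known to be disease-free, and the full data tool is not shown. That is why the disease-free rule above relies on last follow-up and recorded recurrence.
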